² If the dose constraints cannot be achieved with two dose reductions (e.g., 15 Gy reduced to 10 Gy fraction still results in 700 cc of liver not receiving < 15 Gy) then the patient is not evaluable for toxicity or local control, and should be removed from the study.

* Escalation of the two cohorts will be done separately as their tolerance might be substantially different.

Table 2 displays dose levels considered for the study.

1). The primary end-point will be the development of radiation induced liver disease as measured by the > 2-fold worsening of liver functional parameters, clinically apparent worsening of portal hypertension, new or worsening bleeding esophageal varices, or worsening ascites within the first 3 months from initiation of treatment. These will be considered dose-limiting hepatic toxicities. Increases in hepatic enzymes by less than 2-fold alone will not be considered a dose-limiting radiation induced hepatic toxicity if they are not accompanied by other signs of deteriorating liver function as any irradiation of normal liver would be expected to elevate enzymes.

The two patient cohorts will be evaluated separately for determination of toxicity. Deteriorating liver function that can be explained by tumor progression or other non-treatment related events will not be considered a treatment toxicity for the purpose of this analysis.

A dose level will be considered beyond tolerance depending on the fraction of patients who experience a dose-limiting radiation induced hepatic toxicity. See Table 3. Once this happens, enrollment to that dose level will be halted. If this happens at dose level 1, subsequent patients eligible for full dose therapy will enroll into dose level -1. If dose level -1 is found intolerable in patients eligible for full dose therapy, the trial will be stopped.

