3.3 Expected Toxicities

There are a few specific toxicities that are of concern in the irradiation of tumors in the liver. The first concerns the overall maintenance of good hepatic function. From the data in the literature^{4,5}, this appears to be strongly related to the amount of liver in the radiation field treated to moderate dose. The data from liver resection surgery has shown that with a proliferative response, the liver can regenerate itself after removal of ½ or more of the liver. This regeneration will likely not occur if the remaining liver has received a significant amount of radiation, although the dose that would prevent regeneration is not known.

Secondly, the primary biliary radicals could be damaged by the radiation. This would likely be a late response, although initial edema could produce an acute temporary obstruction that would likely be minimized by the use of steroids. Long term, fibrosis could occur producing biliary obstruction.

Third, there can be vascular injury producing a veno-occlusive picture with hepatomegaly and other signs of liver failure that can occur about 3 months after irradiation. In addition, as the liver is in close proximity to multiple normal structures, the tolerance of these structures (liver, lung, esophagus, duodenum) must also be considered as ulceration and necrosis could occur if those structures are irradiated to high dose. Toxicity from structures distant to the radiation beam is very unlikely. Doses to all the above mentioned normal tissues can be calculated during the planning phase of the therapy to allow us to estimate high-risk sites.

These toxicities described above are primarily captured in the CTCAE, Version 3.0 formulation as hepatic and biliary tract related, and they will be measured accordingly. We would not expect toxicities in other organs other than liver, stomach, bowel, or lung. However, all toxicities that are not clearly ascribable to other unrelated causes or to tumor progression will count for the toxicity evaluation.

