7.0 DATA MANAGEMENT AND STATISTICAL ANALYSIS

7.1 Study Design

The primary end-point of this study will be hepatic tolerance to the radiation treatment. This will be complicated by patients who could have progressive disease in the liver that could result in worsening liver function studies. Damage secondary to radiation therapy should appear within 3 months, so that will be the primary time for evaluation. Liver tolerance will be determined by the following:

1). The primary end-point will be the development of radiation induced liver disease as measured by the > 2-fold worsening of liver functional parameters, clinically apparent worsening of portal hypertension, new or worsening bleeding esophageal varices, or worsening ascites within the first 3 months from initiation of treatment. These will be considered dose-limiting hepatic toxicities. Increase in hepatic enzymes by less than 2-fold alone will not be considered a dose-limiting radiation induced toxicity if they are not accompanied by other signs of deteriorating liver function as any irradiation of normal liver would be expected to elevate enzymes.. The two patient cohorts will be evaluated separately for determination of toxicity. Deteriorating liver function that can be explained by tumor progression or other non-treatment related events will not be considered a treatment toxicity for the purpose of this analysis.

A dose level will be considered beyond tolerance depending on the fraction of patients who experience a dose-limiting radiation induced hepatic toxicity. See Table 3. Once this happens, enrollment to that dose level will be halted. If this happens at dose level 1, subsequent patients eligible for full dose therapy will enroll into dose level -1. If dose level -1 is found intolerable in patients eligible for full dose therapy, the trial will be stopped.

Patients will also be evaluated for other unexpected toxicities according to the NCI CTCAE, Version 3.0.. Unexpected Grade 3 toxicities thought to be due to therapy will be scored as 1 and unexpected Grade 4 toxicities thought to be due to therapy will be scored as 2. A patient with both unexpected Grade 3 and Grade 4 toxicities will be counted as a patient with unexpected Grade 4 toxicity. If the total score exceeds 3 in the first 3, 4, or 5 patients, or exceeds 4 at any point within a dose level, enrollment to that dose-level will be halted and that dose will be considered beyond tolerance. See Table 4.

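### The 3-month hepatic DLT window ends at about the time Section 3.3 says veno-occlusive injury can occur, so an unknown share of primary-endpoint events may escape Tables 3 and 5A

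*Combined protocol and SAP*

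**What the plan says.** Section 3.2 defines the primary end-point as radiation-induced liver disease, shown by "> 2-fold worsening of liver functional parameters, clinically apparent worsening of portal hypertension, new or worsening bleeding esophageal varices, or worsening ascites", and counts it only "within the first 3 months from initiation of treatment". Section 7.1 repeats the definition and gives the reason: "Damage secondary to radiation therapy should appear within 3 months, so that will be the primary time for evaluation". Before escalation, Section 3.2 requires each patient in the cohort to be followed for toxicity for 3 months, again counted from the start of therapy.

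Section 3.3 gives a different picture of timing. Vascular injury may produce a veno-occlusive syndrome with hepatomegaly and "other signs of liver failure that can occur about 3 months after irradiation". Of damage to the main bile ducts it says: "This would likely be a late response, although initial edema could produce an acute temporary obstruction".

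The Time and Events Table (5.1) schedules liver function tests at Weeks 4, 8 and 20 after radiation, and Section 5.4 puts liver imaging at Weeks 8 and 20 after completion. Toxicity assessment continues to Week 20 and then every 3 months for 2 years.

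**The concern.** The hepatic DLT count drives both the stopping rule (Table 3) and the escalation rule (Table 5A). If liver injury tends to appear around the close of the window, part of it is dated after the cutoff and does not count, although the protocol goes on collecting it. A dose level could then be called tolerable, or pass Table 5A, because the injury came late.

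The other toxicity rule is not a clear safety net. Tables 4 and 5B count unexpected toxicities only. Section 6.1.2 defines unexpected by inconsistency with the described risk information, and veno-occlusive injury is described under Expected Toxicities. Section 3.3 also says that toxicities without a clear alternative cause count in the toxicity evaluation. It sets no time limit, which does not fit the 3-month cutoff.

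**Working it through.** **The plan's own figures.** The plan states no operating characteristics for Tables 3 or 5A. Its one sample-size figure, 40 evaluable patients, reproduces as 2 cohorts × 2 dose levels × 10 patients. It does not depend on the window.

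**When the window closes.** Inputs: 3 months = 91.3 days from initiation (3.2); course of 5 to 14 days (footnote b to the Time and Events Table).

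- Close of window after the end of radiation: (91.3 − 5)/7 = 12.3 weeks; (91.3 − 14)/7 = 11.0 weeks.
- If 3 months after irradiation is counted from completion, the window closes 5 to 14 days too early. If it is counted from the start, the two coincide.

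**Scheduled tests inside the window.**

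- Week 8 visit, from initiation: (56 + 5)/7 = 8.7 weeks to (56 + 14)/7 = 10.0 weeks.
- Week 20 visit, from initiation: (140 + 5)/7 = 20.7 weeks to (140 + 14)/7 = 22.0 weeks.
- Final part of the window with no scheduled liver test: (91.3 − 61)/7 = 4.3 weeks to (91.3 − 70)/7 = 3.0 weeks.

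A biochemical worsening that begins in those weeks and is first measured at Week 20 would be dated outside the window.

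**What a loss of events does to the rules.** Let p be the true DLT rate, f the share of events counted (assumed), and r = p·f. Counts never fall, so Table 3 stops a level of 10 if there are at least 3 DLTs in the first 5 patients or at least 4 in all 10:

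P(stop) = P(X₁₀ ≥ 4) + 10·r³(1 − r)²·(1 − r)⁵

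Table 5A is met at 10 patients with at most 1 DLT:

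P(≤1 of 10) = (1 − r)¹⁰ + 10·r(1 − r)⁹

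For p = 0.40, which is above the plan's ceiling of 0.33:

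| Events missed (assumed) | r | P(Table 3 stop) | P(≤1 DLT in 10) |
|---|---|---|---|
| 0% | 0.40 | 0.618 + 0.018 = 0.636 | 0.046 |
| 10% | 0.36 | 0.513 + 0.021 = 0.534 | 0.076 |
| 25% | 0.30 | 0.350 + 0.022 ≈ 0.373 | 0.149 |
| 50% | 0.20 | 0.121 + 0.017 = 0.138 | 0.376 |

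At p = 0.33 the same steps give P(stop) 0.45, 0.37, 0.24 and 0.08 for 0%, 10%, 25% and 50% missed (the 10% row uses r = 0.297), and P(≤1 of 10) 0.11, 0.15, 0.25 and 0.49.

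**Which losses are plausible.** Assume that veno-occlusive onset is normal, centred at 3 months, with SD 2 to 6 weeks. Counted from the start of radiation, 50% falls outside the window. Counted from the end of a course of d days, the share is Φ((d/7)/SD), which runs from 55% (5 days, SD 6 weeks) to 84% (14 days, SD 2 weeks). This applies only to veno-occlusive events. If they make up 10%, 25% or 50% of hepatic DLTs, the loss among all DLTs is 5–8%, 13–21% or 25–42%. If Section 7.1 is right about timing, it is near zero.

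**The case against.** A reader might infer that a large part of the expected primary-endpoint events falls outside the window. The documents do not support that. Section 3.3 says only that the veno-occlusive picture can occur at about 3 months, with no frequency or onset distribution. It is the third of three liver concerns listed; the first, loss of overall hepatic function, is given no late timing. A gap of 5 to 14 days is within the imprecision of the word about, and Section 7.1 states the opposite expectation. All of this stands.

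A reader might also count late biliary injury as missed DLTs. Biliary obstruction is not a named component of the end-point and could enter only through worsening liver parameters.

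Meeting Table 5A is not the same as escalating. Table 5B and the local-failure condition also apply, and irradiated lesions have a Week 8 baseline with the next scheduled imaging at Week 20. By then later toxicity will be visible for many patients. The unexpected-toxicity score and the Grade 5 suspension state no 3-month limit, and the teleconferences review toxicity. This limits the harm but does not remove the defect. The stated toxicity wait is still 3 months from initiation, and seeing a later hepatic event does not make it count in Tables 3 or 5A.

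**Conclusion.** The inconsistency is real. Sections 3.3 and 7.1 disagree on when liver injury appears, and the window ends at, or 5 to 14 days before, the time that Section 3.3 names. No liver test is scheduled in the window's last 3.0 to 4.3 weeks. Tables 3 and 5A can therefore miss an unknown and possibly material share of primary-endpoint events.

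The size rests on assumption. At a true rate of 40%, a loss of a quarter of events lowers the chance of a Table 3 stop from 0.64 to 0.37 and triples the chance of at most 1 DLT in 10, from 0.05 to 0.15. A much worse result is possible only on stacked assumptions: if every DLT were veno-occlusive and 30–45% were captured, P(≤1 of 10) would be 0.44–0.66. If such events were a quarter of DLTs, with onset SD 1 month and 32–44% of them captured, it would be 0.09–0.11. The documents do not choose between these cases, and this review does not decide which clinical statement about timing is right.

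**What to change.** Reconcile Sections 3.2, 3.3 and 7.1 so that one onset time is stated, and the DLT window and the pre-escalation wait both cover it. The Week 20 post-radiation visit already has liver tests, imaging and toxicity assessment, so it can close the window without a new visit.

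At minimum:

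- Count treatment-related hepatic events found through Week 20 when Tables 3 and 5A are applied.
- Report the DLT rate both at 3 months and through Week 20.
- State whether a hepatic event after the window counts in Tables 4 and 5B.
- Align adverse-event recording, which Section 6.2 ends 30 days after treatment, so that these events are captured.
- Tabulate late biliary injury by dose level, outside the DLT count.

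If 3 months is kept, Section 3.3 must be made consistent with it, and the untested end of the window needs a scheduled liver assessment, which would be a new visit.

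Cost: moving to Week 20 lengthens the toxicity wait for the last patient from 13.0 weeks to 20.7–22.0 weeks, so by about 8 to 9 weeks. It adds little or nothing where escalation already awaits the 5–6 month local-control evaluation. More events will need attribution between treatment and progression, a difficulty Section 7.1 already recognises. Some bridge-to-transplant patients may not be evaluable at Week 20, so a rule for them is needed.

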Patients will also be evaluated for other unexpected toxicities according to the NCI CTCAE, Version 3.0. Unexpected Grade 3 toxicities thought to be due to therapy will be scored as 1 and unexpected Grade 4 toxicities thought to be due to therapy will be scored as 2. A patient with both unexpected Grade 3 and Grade 4 toxicities will be counted as a patient with unexpected Grade 4 toxicity. If the total score exceeds 3 in the first 3, 4, or 5 patients, or exceeds 4 at any point within a dose level, enrollment to that dose level will be halted and that dose will be considered beyond tolerance. See Table 4. If this happens at dose level 1, subsequent patients eligible for full dose therapy will enroll into dose level -1. If dose level -1 is found intolerable in patients eligible for full dose therapy, the trial will be stopped.

Table 3:

# of patients with a DLT	Total # patients in cohort	Action
≥3	3, 4, 5	Stop dose-cohort ¹
≥4	6, 7, 8, 9, 10	Stop dose-cohort ¹

¹If this occurs within Dose level 1, enter the next group of patients eligible for full dose to Dose level -1. If dose level -1 is found intolerable in patients eligible for full dose therapy, the trial will be stopped.

Table 4:

# of patients with unexpected Grade 3 ¹	# of patients with unexpected Grade 4	Total # patients in cohort	Action
≥0	≥2	3, 4, 5	Stop dose-cohort ²
≥4	≥0		
≥0	≥3	6, 7, 8, 9, 10	Stop dose-cohort ²
≥1	≥2		
≥5	≥0		

¹A patient with both unexpected Grade 3 and Grade 4 toxicities is counted as a patient with unexpected Grade 4 toxicity

²If this occurs within Dose level 1, enter the next group of patients eligible for full dose to Dose level -1. If patients eligible for full dose cannot tolerate dose level -1, the trial will be stopped.

The development of any Gr. 5 toxicity thought related to therapy will result in temporary suspension of the trial for full evaluation. If specific toxicity related to an irradiated organ is found, alteration of the dose parameters for that tissue will be modified, although not necessarily a reduction in the planned tumor dose.

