5.4 Post-treatment Assessments (Up to week 20 after RT Treatment)

- History and physical examination
- Performance status
- Laboratory studies including CBC, and liver function tests
- CT, PET or MRI of the liver will be performed at, 8 and 20 weeks after the completion of radiation therapy and then at regular intervals per Section 5.1.
- Toxicity assessment (NOTE: this should occur up to week 20 regardless of whether disease recurs prior to this point or not).

5.5 Follow-up Assessments:

Follow-up will be done every three months for two years, or until disease progresses in an irradiated liver lesion. If disease progresses in a non-irradiated lesion only, follow-up will continue until disease progresses in one of the irradiated liver lesions. Once disease progresses in an irradiated liver lesion, protocol follow-up will cease other than follow-up of any unresolved treatment-related toxicity. Follow-up assessments will include:

- History and physical examination
- Performance status
- Laboratory studies for liver function tests
- CT, PET or MRI of the liver.
- Toxicity assessment

Patients in whom high dose irradiation is delivered to the main hepatic ducts or common bile duct will be considered for elective stent placement within the first 4 weeks after completion of radiation therapy to prevent biliary obstruction.

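### Tables 4 and 5B count only 'unexpected' Grade 3-4 toxicities and Section 3.3 names no table, so read literally, related GI, lung or non-DLT biliary events can escape every count

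*Combined protocol and SAP*

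**What the plan says.** All places are in the combined protocol and SAP.

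- **Hepatic count (Section 3.2, repeated in 7.1; Tables 3 and 5A).** A DLT is a more than 2-fold worsening of liver parameters or "clinically apparent worsening of portal hypertension, new or worsening bleeding esophageal varices, or worsening ascites within the first 3 months" of starting treatment. Only these events enter Tables 3 and 5A.
- **Other toxicity count (Sections 3.2 and 7.1; Tables 4 and 5B).** "Patients will also be evaluated for other unexpected toxicities according to the NCI CTCAE, Version 3.0". Unexpected related Grade 3 scores 1 and Grade 4 scores 2. Enrolment to a level halts if the total exceeds 3 in the first 3 to 5 patients or exceeds 4 at any point. Tables 4 and 5B use the same qualifier. Goal 2 limits the Grade 3 rate plus twice the Grade 4 rate to 0.4; its wording attaches 'unexpected' to Grade 3 only.
- **Section 3.3, Expected Toxicities.** On biliary injury: "Long term, fibrosis could occur producing biliary obstruction". On nearby structures, including lung, esophagus and duodenum, their tolerance "must also be considered as ulceration and necrosis could occur if those structures are irradiated to high dose". Then: "We would not expect toxicities in other organs other than liver, stomach, bowel, or lung". And finally: "However, all toxicities that are not clearly ascribable to other unrelated causes or to tumor progression will count for the toxicity evaluation". No table or score is named.
- **Section 5.5.** Patients with high dose to the main hepatic or common bile duct are to be considered for "elective stent placement within the first 4 weeks after completion of radiation therapy to prevent biliary obstruction".

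**The concern.** The four tables decide whether a dose level halts and whether the next one opens, and an escalated dose is judged too toxic on Tables 3 and 4 alone. A related Grade 3-4 duodenal ulcer, lung injury or biliary obstruction that is not a hepatic DLT can enter only Tables 4 and 5B, and only if it is called unexpected. Section 3.3 describes these injuries under the opposite heading, yet also says that related toxicities count. Applied as worded, the decision rule and that sentence disagree.

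Lung and biliary events are the clearest cases. Section 3.3 describes both, and Tables 1 and 2 set no lung or bile duct dose limit. The trial is multi-center (Section 6.4), so two sites could classify the same event differently. At stake is the primary objective: a level with substantial severe non-hepatic toxicity could be declared tolerable and escalated.

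**Working it through.** **1. Where each kind of event is counted**

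| Related event | Tables 3 / 5A | Tables 4 / 5B, literal reading | Tables 4 / 5B, broad reading |
|---|---|---|---|
| Listed hepatic DLT within 3 months | Yes | No | No |
| Biliary obstruction within 3 months with >2-fold worsening of liver parameters | Yes | No | No |
| Other Grade 3-4 biliary event | No | Can be left out | Yes |
| Grade 3-4 GI or lung event | No | Can be left out | Yes |

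The broad reading takes 'other unexpected' to mean everything outside the hepatic DLT list.

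**2. The plan's own figure.** The highest score that does not halt a level of 10 patients is 4, and 4/10 = 0.40, which matches goal 2. That limit is not in dispute. The question is which events feed it.

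**3. Inputs for the illustration.** From the plan: 10 patients per level (Section 7.2), the score thresholds and Tables 4 and 5B (Section 3.2). The plan gives no event rates, so the rates below are assumptions. Each patient has Grade 3 only (probability p3), Grade 4 (p4) or neither. 'Half scored' means each event is scored independently with probability 0.5, so both rates halve.

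**4. Rules applied after each patient from the third**

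- Text rule: halt if G3 + 2×G4 > 3 at n = 3-5, or > 4 at n = 6-10.
- Table 4 as printed: halt at n = 3-5 if G4 ≥ 2 or G3 ≥ 4; at n = 6-10 if G4 ≥ 3, or G3 ≥ 1 with G4 ≥ 2, or G3 ≥ 5. Table 4 omits some mixed combinations that the text rule catches, so both results are shown.
- Table 5B at n = 10: G3 ≤ 2 with no G4, or no G3 with one G4.

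Halting probabilities come from exact sequential enumeration. Meeting Table 5B means a final score of at most 2, so no such path has halted earlier and a closed form applies. With q = 1 − p3 − p4:

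P(5B) = q^10 + 10·p3·q^9 + 45·p3²·q^8 + 10·p4·q^9

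At p3 = 0.20, p4 = 0.10, q = 0.70: 0.0282 + 0.0807 + 0.1038 + 0.0404 = 0.2531.

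**5. Results**

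| Assumed Grade 3 + Grade 4 (weighted rate) | Share scored | P(halt), text / Table 4 | P(Table 5B met, no halt) |
|---|---|---|---|
| 5% + 2% (0.09) | all | 0.01 / 0.01 | 0.91 |
| 10% + 5% (0.20) | all | 0.09 / 0.06 | 0.67 |
| | half | 0.02 / 0.01 | 0.89 |
| 20% + 10% (0.40) | all | 0.40 / 0.27 | 0.25 |
| | half | 0.09 / 0.06 | 0.67 |
| 30% + 20% (0.70) | all | 0.85 / 0.71 | 0.03 |
| | half | 0.31 / 0.24 | 0.35 |
| any | none | 0 / 0 | 1.00 |

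**The case against.** The strongest reply is that the sections can be read in harmony. The score sentence follows directly on the hepatic DLT paragraph and says 'other', which may simply mean every event outside that list. Section 3.3 says related toxicities count, and for a non-DLT event Tables 4 and 5B are the only place to count it. The Amendment 1 summary also uses 'expected toxicities' for the hepatic DLTs. On this reading nothing is lost.

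Other text points the same way. The end of Section 3.3 says acute toxicities are not anticipated, so a GI or lung event within a week of radiation may be unexpected on the plan's own words. Section 6.1.2 lets an event be unexpected because of its severity, and 3.3 assigns no grades. Stents are only considered, and only for high duct dose; Cohort 1 is limited to peripheral lesions.

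There are also safeguards outside the tables. Any related Grade 5 event suspends the trial. GI structures have dose limits. Section 3.2 adds: "If specific toxicity related to an irradiated organ is found, alteration of the dose parameters for that tissue will be modified". Acute Grade 3 or higher events are reviewed by organ, and team calls and the monitoring committee review the study.

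Most of this stands. A reader might infer that the plan excludes all GI, lung and biliary toxicity from its decisions, or that Table 4 can never halt a level. The documents do not support that: they allow the exclusion but do not require it. What remains is that neither 3.2 nor 7.1 says which reading governs the score, and none of the Grade 3-4 safeguards supplies a count.

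**Conclusion.** The point holds as a conflict between a decision rule as worded and Section 3.3. Related Grade 3-4 GI, lung or non-DLT biliary events can be left out of every halting and escalation count. It is worth fixing because the affected counts define a tolerable dose.

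The size depends on two things that the plan does not give: the true rates and the reading in use. If the team already scores all non-DLT events, the effect is zero. The contrast between all and none scored is an upper bound. At goal 2's limit (20% + 10%) that bound is 0.40/0.27 in halting and 0.75 (1.00 − 0.25) in meeting Table 5B. At 5% + 2% it is about 0.01 and 0.09 (1.00 − 0.91). Meeting Table 5B does not by itself open the next level: Table 5A and the local-failure condition must also be met.

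A reader might also infer that late biliary injury calls for new rules, such as adding late events to completed levels or reviewing higher levels. That is a separate question of the observation window and does not follow from this defect.

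**What to change.** In the score sentences of 3.2 and 7.1, in Tables 4 and 5B, and in goal 2 for both grades, replace 'unexpected' with 'therapy-related and not already counted as a hepatic DLT'. Have the final counting sentence in 3.3 cite Tables 4 and 5B. Keep the existing 3-month evaluation before escalation.

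The cost is wording only. Toxicity assessments are already scheduled during treatment and at weeks 1, 4, 8 and 20 after it, so no visits are added. If the broad reading was intended, the edit merely records it.

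If the narrow reading was in use, levels will halt more often or escalate less often. At 10% + 5%, halting rises by at most 0.09 (text rule) or 0.06 (Table 4), and the chance of meeting Table 5B falls to 0.67 from at most 1.00. The change is larger at higher rates: at 20% + 10%, which still satisfies goal 2, halting rises by up to 0.40/0.27 and Table 5B is met with probability 0.25. The team should accept that consequence knowingly when it adopts the wording.
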